4.2 Exclusion Criteria

A subject who meets any of the following criteria is ineligible for the study:

1. Received cytotoxic chemotherapy, radiation therapy, or targeted therapy (including investigational cytotoxic chemotherapy) or biologic agents (e.g., cytokines or antibodies), or other investigational agent within 28 days of study enrollment.
2. For patients who received mitotane within 6 months of consenting, mitotane should have been stopped at least 28 days prior to study enrollment **AND** to have mitotane serum level of < 2 mg/L.
3. Prior treatment with cabozantinib or other cMET inhibitors
4. Known brain metastases or cranial epidural disease unless adequately treated with radiotherapy and/or surgery (including radiosurgery) and stable for at least 4 weeks before the first dose of study treatment. Eligible subjects must be neurologically asymptomatic and without corticosteroid treatment at the time of the start of study treatment.
5. The subject has not recovered to baseline or CTCAE \leq Grade 1 from toxicity due to all prior therapies except alopecia and other non-clinically significant AEs.
6. Prothrombin time (PT)/ International Normalized Ratio (INR) or partial thromboplastin time (PTT) test $\geq 1.3 \times$ the laboratory ULN within 28 days before the first dose of study treatment.
7. Concomitant anticoagulation with coumarin agents (e.g., warfarin), direct thrombin inhibitors (e.g., dabigatran), direct factor Xa inhibitor betrixaban, or platelet inhibitors (e.g., clopidogrel). Allowed anticoagulants are the following:
 - a. Prophylactic use of low-dose aspirin for cardio-protection (per local applicable guidelines) and low-dose low molecular weight heparins (LMWH).
 - b. Therapeutic doses of LMWH or anticoagulation with direct factor Xa inhibitors rivaroxaban, edoxaban, or apixaban in subjects without known brain metastases who are on a stable dose of the anticoagulant for at least 1 week before first dose

Proprietary Information of MD Anderson

of study treatment without clinically significant hemorrhagic complications from the anticoagulation regimen or the tumor.

8. Severe and uncontrolled Cushing syndrome despite medical management (e.g.: systolic blood pressure $>160\text{mmHg}$ or hyperglycemia with fasting glucose above 300mg/dL).
9. The use of strong CYP3A4 inhibitor (with the exception of ketoconazole).
10. The subject has experienced any of the following: a. clinically-significant gastrointestinal bleeding within 6 months before the first dose of study treatment; b. hemoptysis ≥ 0.5 teaspoon(2.5 mL) of red blood within 3 months before the first dose of study treatment; c. any other signs indicative of pulmonary hemorrhage within 3 months before the first dose of study treatment. Tumor invading any major blood vessel at the time of study enrollment.
11. Evidence of tumor invading the GI tract (esophagus, stomach, small or large bowel, rectum or anus), or any evidence of endotracheal or endobronchial tumor within 28 days before the first dose of cabozantinib, or the subject with radiographic evidence of cavitating pulmonary lesion(s); or subjects with tumor invading or encasing any major blood vessels.
12. Uncontrolled, significant concurrent or recent illness including, but not limited to, the following conditions: *a. Cardiovascular disorders* including i. Congestive heart failure (CHF): New York Heart Association (NYHA) Class III (moderate) or Class IV (severe) at the time of screening ii. Concurrent uncontrolled hypertension defined as sustained BP > 150 mm Hg systolic, or > 90 mm Hg diastolic despite optimal antihypertensive treatment within 7 days of the first dose of study treatment iii. Any history of congenital long QT syndrome or iv. Any of the following within 6 months before the first dose of study treatment: • unstable angina pectoris • clinically-significant cardiac arrhythmias • stroke (including TIA, or other ischemic event) within 90 days of the first dose of study treatment • myocardial infarction • clinically significant thromboembolic event within 42 days of randomization requiring therapeutic anticoagulation. (Note: subjects with a venous filter (e.g. vena cava filter) are not eligible for this study) *b. Gastrointestinal disorders* particularly those associated with a high risk of perforation or fistula formation including: i. Any of the following within 28 days before the first dose of study treatment • intra-abdominal tumor/metastases invading GI mucosa • active peptic ulcer disease; patients must be completely recovered • inflammatory bowel disease (including ulcerative colitis and Crohn's disease), acute pancreatitis, pancreatic duct or common bile duct obstruction, acute diverticulitis, acute cholecystitis, symptomatic cholangitis or recent appendicitis within 1 month of first dose of cabozantinib; patients must be completely recovered from these conditions • clinically significant malabsorption syndrome, *c. Endocrine disorders*, uncontrolled Cushing syndrome despite of adequate medical therapy
13. Any of the following within 6 months before the first dose of study treatment: • abdominal fistula • gastrointestinal perforation • bowel obstruction or gastric outlet obstruction • intra-abdominal abscess. Note: Complete resolution of an intra-abdominal abscess must be confirmed prior to initiating treatment with cabozantinib even if the abscess occurred more than 6 months before the first dose of study treatment. • Other disorders associated with a high risk of fistula formation including PEG tube placement within 90 days before the first dose of study therapy
14. Other clinically significant disorders such as: i. active infection requiring systemic antibiotic treatment within 14 days before the first dose of study treatment ii. serious non-healing wound/ulcer/bone fracture within 28 days before the first dose of study treatment iii. history of

Proprietary Information of MD Anderson

organ transplant iv. Concurrent uncompensated hypothyroidism or thyroid dysfunction (TSH above 10) within 28 days before the first dose of study treatment v. Major surgery within 12 weeks before the first dose of study treatment. Complete wound healing from major surgery must have occurred 1 month before the first dose of study treatment. Minor surgery within 28 days before the first dose of study treatment with complete wound healing at least 10 days before the first dose of study treatment. Subjects with clinically relevant ongoing complications from prior surgery are not eligible.

15. Unable to swallow tablets
16. A corrected QT interval calculated by the Fridericia formula (QTcF) >500 milliseconds within 28 days before first dose of study treatment.
17. Pregnant or breastfeeding.
18. A previously identified allergy or hypersensitivity to components of the study treatment formulation.
19. Unable or unwilling to abide by the study protocol or cooperate fully with the investigator or designee.
20. Evidence within 2 years of the start of study treatment of another malignancy which required systemic treatment except for breast ductal carcinoma-in situ, cured non-melanoma skin cancer, or cured in situ cervical carcinoma
21. Any other severe acute or chronic medical or psychiatric condition or laboratory abnormality which, in the judgment of the investigator, would have made the patient inappropriate for entry into this study.

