3.3.2 Warnings and Precautions and Guidelines for the Management of Adverse Events

The most frequent adverse events experienced by $\geq 20\%$ of subjects treated with cabozantinib were diarrhea, fatigue, nausea, decreased appetite, vomiting, weight decreased, PPES, constipation, hypertension, dysgeusia, dysphonia, and asthenia.

Adverse events associated with laboratory abnormalities experienced by $\geq 5\%$ of subjects treated with cabozantinib include anemia, AST increased, ALT increased, hypothyroidism, hypokalemia, hypomagnesemia, thrombocytopenia, hypocalcemia, hypophosphatemia, lipase increased, lactate dehydrogenase (LDH) increased, neutropenia, ALP increased, hyponatremia, and leukopenia. Mild to moderate QTc interval prolongation (10-15ms) has also been observed with a QT interval calculated by the Fridericia formula (QTcF) not exceeding 500 ms. Prolonged QTc appears to be a very rare event and no torsades de pointes have been reported (see latest version of the Investigator Brochure).

Subjects may also experience medically important but less frequent adverse events including arterial and venous thrombotic AEs (eg, DVT, pulmonary embolism [PE], transient ischemic attack [TIA], and myocardial infarction [MI]), severe hemorrhagic events, proteinuria, wound healing complications, GI perforation, abscesses including intra-abdominal and pelvic abscess, GI and non-GI fistulae formation, osteonecrosis, and reverse posterior leukoencephalopathy syndrome (RPLS).

Cabozantinib treatment should be permanently discontinued for the following adverse events: visceral perforation or fistula formation, severe hemorrhage, serious arterial thromboembolic events, nephrotic syndrome, malignant hypertension, hypertensive emergency, persistent uncontrolled hypertension despite optimal medical management, osteonecrosis of the jaw (ONJ), and RPLS.

Guidelines for the management of AEs (i.e., dose interruptions and dose reductions) are presented in the next sections. Each dose reduction of cabozantinib should be to one dose level lower than the current dose. Dose reductions of more than one dose level are acceptable per Investigator judgment. All AEs should also be managed with supportive care at the earliest signs of toxicity. Adverse reactions are presumed to be attributable to study drug. Adverse events classified as “not related” are defined as AEs that are, without question, not associated with the study treatment and definitely attributable to another cause.

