3.3.2.15 GI Perforation/Fistula and Non-GI Fistula Formation

Gastrointestinal perforation/GI fistula: Prior to initiation of treatment with cabozantinib, subjects should be carefully evaluated for potential risk factors including (but not limited to) the following:

- Tumors invading GI or respiratory tracts
- Active peptic ulcer disease, inflammatory bowel disease (eg, ulcerative colitis, Crohn's disease), diverticulitis, cholecystitis or symptomatic cholangitis, or appendicitis
- History of abdominal fistula, GI perforation, bowel obstruction, or intra-abdominal abscess
- Ongoing visceral complications from prior radiation therapy
- Prior GI surgery (particularly when associated with delayed or incomplete healing)

Complete healing following abdominal surgery and/or resolution of intra-abdominal abscess must be confirmed prior to initiating treatment with cabozantinib.

After starting cabozantinib, subjects should be monitored for early signs of GI perforation such as abdominal pain, nausea, emesis, constipation, and fever especially if known risk factors for developing GI perforation or fistula are present.

Discontinue cabozantinib treatment in subjects who have been diagnosed with GI perforation/fistula.

Non-GI fistula formation: Complications from radiation therapy has been identified as a possible predisposing risk factor for fistula formation in subjects undergoing treatment with cabozantinib.

Subjects with any clinically relevant ongoing complications from prior radiation therapy (ie, radiation esophagitis or other inflammation of the viscera) should not be treated with cabozantinib.

Radiation therapy to the thoracic cavity (including mediastinum) should be avoided within 3 months of starting treatment with cabozantinib (excluding local radiation for bone metastases). Fistula should be ruled out as appropriate in cases of onset of severe mucositis or difficulty swallowing after start of therapy. Discontinue cabozantinib and initiate appropriate management in subjects who have been diagnosed with a non-GI fistula.

Discontinue cabozantinib treatment in subjects who have been diagnosed with non-GI fistula.

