5 STUDY ASSESSMENTS AND PROCEDURES

5.1 Pre-Treatment Period

- During the Pre-Treatment Period, during which the participant will follow the schedule found in table 5-1, subjects are consented and qualified (screened) for the study. Informed consent must be obtained before initiation of any clinical screening procedure that is performed solely for the purpose of determining eligibility for this study. Evaluations performed as part of routine care before informed consent can be considered as screening evaluations if done within the defined screening period, and if permitted by the site's institutional review board (IRB)/ethics committee (EC) policies. Study eligibility is based on meeting all of the study inclusion criteria and none of the exclusion criteria at screening and on Study Day 1 before study treatment administration. The following assessments will be conducted before subjects receiving their first dose of cabozantinib on this protocol:

1. For patients with measurable visceral metastases CT scans with contrast or MRI including chest/abdomen/and pelvis are required.
2. Demographics
3. Medical and cancer history/demographics
4. Height
5. Weight
6. Vital Signs
7. ECOG Performance Status

Proprietary Information of MD Anderson

8. Clinical laboratory testing

- chemistry panel (albumin, alkaline phosphatase, ALT, AST, bicarbonate, blood urea nitrogen, calcium, chloride, creatinine, glucose, , magnesium, phosphorus, potassium, sodium, total bilirubin, total protein)
- hematology tests(CBC, differential, platelets)
- adrenal hormonal assessment
- urinalysis and UPCR
- thyroid function tests (TSH, free T4)
- pregnancy test (urine or serum) for women of child-bearing potential
- PT/INR, PTT
- Serum mitotane level if used mitotane within 6 months

9. ECGs

10. Physical examination, safety and adverse events evaluation will be performed at baseline.

For each subject, the Pre-Treatment Period ends upon receipt of the first dose of study treatment or final determination that the subject is ineligible for the study.

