5.2 Treatment Period

During the Treatment Period subjects will receive cabozantinib until either disease progression, the occurrence of unacceptable drug-related toxicity or for other reason(s) for subject withdrawal as described in Section 2.5. Subjects should be instructed to immediately inform the principal investigator (PI) of any AEs. Subjects experiencing dizziness, sleepiness, or other symptoms that could influence alertness or coordination should be advised not to drive or operate other heavy machinery.

The following schedule of assessments applies to all subjects (Table 5-1). More frequent assessments should be obtained if clinically indicated.

Proprietary Information of MD Anderson

Table 5-1: Study Assessments

				Study Treatment Period			Post-Treatment Period
	Within 28 days before 1 st Dose of Study Treatment	Day 1	Day 1 of Weeks 3, 5, then every 4 weeks (± 5 days)	Day 1 of Week 5 (± 5 days)	Day 1 of Week 9 (± 5 days)	At Progression (+ 5 days)	30 - 37 Days after last dose
Informed consent	X						
Demographics	X						
Medical and cancer history/demographics	X						
Physical examination	X		X				X
Height	X						
Weight	X		X				X
Vital signs	X		X				X
ECOG performance status	X		X				X
Clinical laboratory tests ¹	X		X ²				X
Urinalysis and UPCR ¹⁰	X		X ²				X
PT/INR, PTT	X		X ¹²				
TFTs (TSH, free T4)	X		X ²				
12-lead ECG ⁸	X		X				X
Cabozantinib administration		X	X (daily)				
Pregnancy test	X	X ⁹	X ²				X
Tumor assessment ³	X		X (every 8 weeks)				
Adrenal hormonal profile ⁴	X		X (every 8 weeks)				
Serum mitotane level ⁵	X						
Concomitant medications	X	X	X				X
Adverse events	Continuous						X
Immunologic assessments ¹¹	X ¹¹				X ¹¹	X ¹¹	
Pharmacogenetic assessment ¹¹	X ¹¹						
Pharmacokinetic assessment ⁶		X ⁶		X ⁶			
Optional biopsy ⁷	X ⁷			X ⁷		X ⁷	

Proprietary Information of MD Anderson

ECG, electrocardiogram; ECOG, Eastern Cooperative Oncology Group; PT/INR, prothrombin time/International Normalized Ratio; PTT, partial prothrombin time, TFT, thyroid function test; UPCR, urine protein/urine creatinine ratio

¹Laboratory tests should include a standard hematology panel (CBC, differential, platelets) and chemistry panel (albumin, alkaline phosphatase, ALT, AST, bicarbonate, blood urea nitrogen, calcium, chloride, creatinine, glucose, , magnesium, phosphorus potassium, sodium, total bilirubin, total protein)

²Every 8 weeks (+/- 5 days) after the first 12 weeks

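### The single 28-day radiation washout in Exclusion 1 leaves out the protocol's own 3-month precaution on thoracic radiation

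*Combined protocol and SAP*

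**What the plan says.** Section 4.2, item 1 excludes anyone who "Received cytotoxic chemotherapy, radiation therapy, or targeted therapy", a biologic agent "or other investigational agent within 28 days of study enrollment". Radiation is named without regard to site, and the 28 days are counted to enrollment.

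Section 3.3.2.15, under non-GI fistula, describes complications of radiation as a possible predisposing factor and then states: "Radiation therapy to the thoracic cavity (including mediastinum) should be avoided within 3 months of starting treatment with cabozantinib". Local radiation for bone metastases is exempt. The same section says that patients with clinically relevant ongoing radiation complications should not receive the drug.

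Section 5.1 sets the test for entry: "Study eligibility is based on meeting all of the study inclusion criteria and none of the exclusion criteria at screening", and again on Day 1 before dosing.

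Section 3.3.2 gives the consequence of a fistula: "Cabozantinib treatment should be permanently discontinued for the following adverse events: visceral perforation or fistula formation".

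**The concern.** A precaution about how soon after chest radiation the drug may be started can act only before the first dose, so it belongs in the screening check. Here it appears only in the section on managing adverse events, while the eligibility lists apply a shorter, site-blind interval. Staff who screen from 4.1 and 4.2 would have no prompt to ask about chest radiation given five to twelve weeks earlier.

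What is at stake is patient safety at entry. Fistula ends treatment permanently, and Section 3.3.2.14 separately lists recent thoracic radiation as a risk factor for hemorrhage. The primary endpoint, the maximum of 18 patients and the stopping boundaries are unaffected.

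**Working it through.** No design figure is involved. The check is a comparison of the two rules, followed by a count of the days between them.

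**1. Is the 3-month interval anywhere in 4.1 or 4.2?** The candidates are:

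- Item 1: 28 days for all radiation.
- Item 5 and Inclusion 5: these concern unresolved toxicity. Item 5 asks for recovery to baseline or "Grade 1 from toxicity due to all prior therapies except alopecia and other non-clinically significant AEs". Neither sets a time since radiation.
- Item 12: uncontrolled or recent illness, including GI disorders. It does not name radiation.
- Item 13: fistula, perforation, obstruction, abscess, and other disorders with high fistula risk such as a PEG tube placed within 90 days. It does not name radiation.
- Item 21: investigator judgment about a severe condition or laboratory abnormality. It gives no interval.

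A patient without symptoms who had mediastinal radiation six weeks (42 days) before same-day enrollment and dosing meets none of these exclusions by their terms.

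**2. Were the other risk factors in 3.3.2.15 carried over?** Most were. Tumor invading the GI tract or airways is in item 11, peptic ulcer and inflammatory bowel disease in item 12b, and surgery and healing in item 14. Fistula, perforation, obstruction and abscess are in item 13, which even repeats the abscess check: "Complete resolution of an intra-abdominal abscess must be confirmed prior to initiating treatment with cabozantinib". The thoracic-radiation interval is the only time window that 3.3.2.15 states, and it was not carried over.

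**3. Size of the gap.** Inputs:

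- Washout of 28 days to enrollment (4.2, item 1).
- Precaution of 3 months to the start of treatment (3.3.2.15), taken as 91 days; the calendar range is 89 to 92.
- d = days from enrollment to first dose. The documents do not fix d. Table 5-1 puts consent in the column headed "Within 28 days before 1 st Dose of Study Treatment". If enrollment is no earlier than consent, d runs from 0 to 28. That upper limit is an assumption.

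Radiation passes item 1 if given at least 29 days before enrollment, that is, at least 29 + d days before the first dose. The uncovered band runs from day 29 + d to day 91, counted inclusively:

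width = 91 − (29 + d) + 1 = 63 − d

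| d (days) | Band before first dose | Width (days) |
|---|---|---|
| 0 | 29 to 91 | 63 |
| 7 | 36 to 91 | 56 |
| 14 | 43 to 91 | 49 |
| 28 | 57 to 91 | 35 |

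With 3 months taken as 89 to 92 days, the width is 61 to 64 at d = 0 and 33 to 36 at d = 28. No lag in this range closes the gap.

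**4. A smaller mismatch.** Item 14 excludes clinically relevant ongoing complications of surgery but does not mention radiation, although 3.3.2.15 says such radiation complications should rule out treatment. Item 5 and Inclusion 5 cover most of these. What is left is a complication at Grade 1 or baseline that is still clinically relevant.

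**The case against.** The strongest reply is that a precaution and an exclusion may differ by design. Section 3.3.2.15 advises and does not prohibit. Parts of Section 3.3.2 read as general cabozantinib guidance, so 4.2 could be the trial's deliberate choice. Section 3.3.2.14 already asks for recent thoracic radiation to be considered before treatment, and nothing in 5.1 says that such advice lapses once the lists are met. The affected group is narrow: bone-directed radiation is exempt, and items 10 and 11 already remove recent hemoptysis, endobronchial tumor, cavitating lung lesions and vessel invasion. The interval is also not explicitly placed before the first dose. Finally, a cross-reference on the eligibility checklist would keep the discretion that a hard exclusion removes.

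Part of this stands. The wording is advisory, the number affected is unknown and may be small, and the documents do not prove an oversight. The rest does not close the gap. Section 3.3.2.14 concerns bleeding and gives no interval. The sentence before the precaution concerns prior radiation complications, so time before the first dose is the natural reading; if time afterward is meant as well, the screening gap remains. A hard window would not be out of place, since 4.2 already uses 3 months for hemoptysis (item 10) and 90 days for PEG placement because of fistula risk (item 13). A checklist cross-reference would help, but it would leave 4.2 and 3.3.2.15 giving different intervals.

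**Conclusion.** The concern holds. The eligibility criteria admit patients whose thoracic or mediastinal radiation falls inside the window the protocol itself advises avoiding. The uncovered band is at most 63 days, and 35 days if enrollment precedes dosing by 28. This rests on reading the interval as time before the first dose, on 3 months being about 91 days, and on the assumed 28-day limit on the lag. It is a safety alignment point that should be corrected. The item 14 mismatch is minor.

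**What to change.** In 4.2 item 1, add an exclusion for radiation to the chest cavity, mediastinum included, in the 3 months before the first dose, with local treatment of bone metastases exempt. Keep 28 days for all other radiation. As a minor alignment, add three words (or radiation therapy) to the item 14 sentence on surgical complications. Add one line to the eligibility checklist. If the sponsor judges 28 days sufficient for thoracic fields, it should say so and revise 3.3.2.15, so that the two sections agree.

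The drafting cost is trivial. The real cost falls on an occasional patient who must wait, at most about 2 months (63 days). Section 1.1 gives a median time to progression of about 2 months on second-line therapy, so for some patients waiting may mean not being enrolled.
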